Exclusion criteria for both: Any major unstable medical/psychiatric illness (e.g., hospitalization within 90 days, suicide risk, etc.); severe clinical depression/anxiety (with PHQ-9 scores >20); chronic pain condition (e.g., fibromyalgia, migraines for healthy controls, etc.) or sensory abnormalities (e.g., neuropathy, Raynaud's, etc.); current regular (weekly or more often) practice of meditation or other mind-body intervention; diagnosis of medication overuse headache or chronic migraine. Migraineurs will be studied if they have been headache-free the day of the study visit. Participants may be currently taking migraine medications, as long as they do not have a diagnosis of medication overuse headache. Volunteers with no pain ratings to frankly noxious stimuli (temperatures > 49°C) or excessive responses to threshold temperatures (~43°C) will be excluded. Pregnant subjects will be excluded from all portions of the study due to possible unknown risks of frankly noxious stimuli. Due to unknown risks and potential harm to the unborn fetus, sexually active women of childbearing potential must use a reliable method of birth control while participating in this study. Reliable methods of birth control are: abstinence (not having sex), oral contraceptives, intrauterine device (IUD), DepoProvera, tubal ligation, or vasectomy of the partner (with confirmed negative sperm counts) in a monogamous relationship (same partner). An acceptable, although less reliable, method involves the careful use of condoms and spermicidal foam or gel and/or a cervical cap or sponge.

Table 1: Migraine Diagnosis*

- | |
|--|
| 
• At least 5 attacks, not attributable to another disorder, with:
• Headache lasting 4-72 hours (untreated or unsuccessfully treated)• Headache with at least 2 of the 4:
• Unilateral location• Pulsating quality• Moderate or severe pain intensity• Aggravation by or causing avoidance of routine physical activity (e.g. walking or climbing stairs)• During headache at least 1 of the 2:
• Nausea and/or vomiting• Photophobia and phonophobia |
|--|

*According to the International Classification of Headache Disorders-II Guidelines

Study Enrollment Procedures

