- Full Neurology evaluation to confirm diagnosis and inclusion/exclusion criteria

STUDY INTERVENTIONS

Interventions, Administration, and Duration

There will only be ONE study visit, which will have 3 parts.

Study Visit (Parts A, B, C):

Part A: Participants will meet with a member of the study team to: 1) review study protocol; 2) obtain informed consent; 3) obtain detailed health history/exam to confirm inclusion/exclusion criteria.

Part B: Psychological Measures: Before the experimental session, participants will use REDCap to complete the questionnaires (see Table 6 for migraineurs and Table 7 for healthy volunteers).

Part C: Experimental Session of Quantitative Sensory Testing (QST) Measurements:

Thermal Probe: MEDOC TSA-II will deliver thermal stimuli with a 16 x 16 mm thermal probe. All temperatures will be < 50°C and no stimulus as designed produces tissue damage. We have significant experience using this technique and probe with no adverse events ([name]'s lab on > 750).

Psychophysical Training: To gain experience rating pain, subjects will be familiarized with 32, 5-second duration stimuli (35 to 49°C) with the Visual Analogue Scale (VAS), a 15 cm plastic sliding scale used to quantify pain sensation intensity and degree of unpleasantness.³⁷ The VAS is an ideal pain measurement scale because of its ratio scale properties combined with its ease of administration and scoring.³⁸ The minimum rating is “no pain sensation” or “not all unpleasant” whereas the maximum is designated as “most intense imaginable” or “most unpleasant imaginable.” The training will be conducted on the left arm, a location away from increased sensitivity/allodynia of head/neck regions often seen in patients with migraines.

Pain Threshold Assessment: The temperature of the probe will begin at 32°C and will increase at a rate of 0.5°C per second. The subject will be instructed to verbally respond when he or she first detects a sensation of pain. The thermode will return to baseline once the button is pressed. This will be performed up to four times, and the heat pain threshold will be determined as the average of the temperatures at which the stimulus was first perceived as painful ([Yarnitsky and Sprecher, 1994](#)). Stimulus temperatures employed for pain threshold testing will not exceed 50°C. This will be conducted on the right arm.

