Affective components of pain may be targeted in ways that do not involve medication, which is highly desirable in a condition that is persistent throughout a lifetime and principally affects women of childbearing potential. Research has demonstrated that meditation, a non-pharmacological intervention, differentially decreases the affective over sensory responses to experimental pain in healthy controls. After learning to meditate, one's experience of pain is altered, with diminished affective responses to pain. We will be able to evaluate this effect in the clinical pain condition of migraine by determining if a meditation intervention taught to migraineurs differentially decreases the affective responses over the sensory responses to experimental pain. This work will be a novel contribution that demonstrates the specific mechanisms of meditation-induced pain relief in migraine patients. In summary, distinguishing the sensory from affective components of pain in our research will help us determine if QST measurements can be used as a target for treatment. This ultimately will help us further understand the mechanisms of meditation induced pain relief and allow for more precise, targeted treatment options.

Further, medications alone rarely target the affective/cognitive processes that often play a major role in migraine pain and disability. Because of this high affective/cognitive burden of migraine pain, we hypothesize that therapies that target these factors may be especially beneficial and may differentially impact the affective component of migraine pain. For example, cognitive behavioral therapy (CBT) is efficacious (with Grade A evidence) for migraine prevention.⁶⁷⁻⁷⁰

Mindfulness-Based Stress Reduction (MBSR) has beneficial effects on many health outcomes, including chronic pain conditions.^{42-49,71-74} MBSR is a standardized course in mindfulness meditation and yoga.⁷⁵ Mindfulness meditation involves both 1) focused attention on a sensation like the breath while non-judgmentally disengaging from distracting thoughts; and 2) open monitoring, with non-reactive present-moment awareness of sensory stimuli.⁷⁶ These practices

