
 •Current regular (weekly or more often) practice of meditation or other mind-body intervention •Any major unstable medical/psychiatric illness (e.g., hospitalization within 90 days prior to screening, suicide risk, etc.) •Other non-migraine chronic pain condition (e.g., fibromyalgia, low back pain, etc.) or sensory nerve problems (e.g., neuropathy, Raynaud’s, etc.) •Diagnosis of medication overuse headache (International Classification of Headache Disorders-II) •Volunteers with no pain ratings to frankly noxious stimuli (temperatures > 49°C) or excessive responses to threshold temperatures (~43°C) •Current or planned pregnancy or breastfeeding •Any new medication started within four weeks of screening visit •Unwilling to maintain stable current medication dosages for duration of trial •Failure to complete baseline headache logs

Study Enrollment Procedures

Recruitment: We will recruit 7 participants every 3 months over the 42 month recruitment period. The study will be run in 6 cohorts. Once ~16 participants meet criteria via phone screening, they will be re-evaluated at the in-person screening visit (see below) to ensure they still meet inclusion criteria. After the screening visit, they will begin keeping their 4 week

headache log (see below); once completed, final determination of inclusion and randomization will occur. Recruitment will continue until sample size goals are reached. We will assume ~10% dropout (conservative estimate given our 0% dropout rate in our pilot trial), so will aim to recruit 98 participants for a final sample of 88 participants. (There may be some overlap of the migraineurs with Part 1).

Screening Visit: The study staff will consent participants, confirm migraine diagnosis with history/neurological exam (will include Structured Diagnostic Interview for Headache), and have participants 1) confirm that no pain relieving medications within 12 hours of study visit, 2) complete baseline questionnaires if they have not been completed at home; 3) complete quantitative sensory testing (QST) as described in Part 1; and 4) learn how to capture daily migraine information using REDCap electronic data capture tools (or iPod touches for those without internet access). Participants will track migraines x 4 weeks to 1) confirm diagnosis; 2) confirm ability to log daily; and 3) use as the 4 week “pre-trial” baseline migraine data.

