Randomization: Once 4-week migraine logs are reviewed by study staff to ensure eligibility, participants will be randomized 1:1 to either MBSR or the control group, stratified by migraine frequency (low frequency of 4-9 headaches/month or high frequency of 10-20 headaches/month). Treatment assignments will be generated by a permuted blocks method with randomly varying block size and sealed in numbered, opaque envelopes. [name] will generate the randomization (using SAS program “PROC PLAN” statement). Participants in both groups will continue to track their migraines with their daily REDCap logs for the duration of the trial.

STUDY INTERVENTIONS

Interventions, Administration, and Duration

Interventions and Interactions

The MBSR Intervention: The PI has conducted 2 previous RCTS with MBSR and is a trained MBSR instructor. The MBSR instructor for this trial (not the PI to avoid bias) has been trained in the structured protocol created by [name].⁹⁵ Given the feasibility of our pilot trial, we anticipate that this population will have no difficulty engaging in the standardized protocol. The participants will meet weekly for 8 weeks for 2.5 hours, plus a “mindfulness retreat day” (approximately 6 hours) after the 6th class [9 total classes.] Mindfulness is cultivated through meditation, body scan (sequential attention to parts of the body), and mindful movement (bodily awareness during gentle stretching, based on hatha yoga). Participants can share their mindfulness experiences with others. The instructor also gives information about stress and stress relief. Participants are advised to incorporate mindfulness into their daily lives so that routine activities (brushing teeth, taking a shower, etc.) become a meditative practice. Each participant will be given the same standard guided audio recordings and encouraged to practice at home for 30-45 minutes per day, at least 5 additional days per week. Compliance will be monitored through class attendance and by daily logs of home practice (using REDCap). Once the course is completed, the participants will be advised to continue in their daily practice.

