After 8 weekly classes have concluded, study participants will be incentivized to keep daily headache logs as follows:

1. For each DAY that the participant keeps their headache log on time, their name will be entered into a drawing (will have the chance to get their name in the drawing up to 30 times in a month)
2. At the end of the month, a name will be drawn and a winner will receive a \$50 Amazon gift card

STUDY PROCEDURES

Table 6 - Summary of Schedule of Evaluations – Part 1 – Migraineurs

Assessment	Telephone Screen	Study Visit
Confirm Eligibility	X	X
Review Study Protocol	X	X
Sign ICF		X
Allodynia Symptom Checklist		X
DERS		X
PCS		X
GAD-7		X
PHQ-9		X
CPAQ		X
HIT-6		X
MIDAS – one month		X
HA management self-efficacy		X
MSQOL		X
Mindfulness, FFM		X
PSS		X
Herth Hope Index		X
Life Orientation Test		X
Social Connectiveness Scale		X
Flourishing Scale		X
Brief Resilience Scale		X
NIH-Promis Measures of Sleep Disturbance		X
NIH-Promis Measures of Global Health (first question only)		X
Pittsburgh Sleep Quality Index		X
QST Measurements		X
Pain Threshold Testing		X
Vitals		X

QST – Quantitative Sensory Testing

Table 7 - Summary of Schedule of Evaluations – Part 1 – Healthy Volunteers

Assessment	Telephone Screen	Study Visit
------------	------------------	-------------

Confirm Eligibility	X	X
Review Study Protocol	X	X
Sign ICF		X
Allodynia Symptom Checklist		X
DERS		X
PCS		X
GAD-7		X
PHQ-9		X
Mindfulness, FFM		X
PSS		X
Herth Hope Index		X
Life Orientation Test		X
Social Connectiveness Scale		X
Flourishing Scale		X
Brief Resilience Scale		X
NIH-Promis Measures of Sleep Disturbance		X
NIH-Promis Measures of Global Health (first question only)		X
Pittsburgh Sleep Quality Index		X
QST Measurements		X
Pain Threshold Testing		X
Vitals		X

QST – Quantitative Sensory Testing

Table 8: Summary of Schedule of Evaluations-Part II

Assessment	Telephone Screen	Screening/ Baseline Visit	Phone Call post 4 week baseline Headache log	Initial F/U	3mo follow-up	6 mo follow-up
Inclusion/Exclusion Criteria	X	X				
Enrollment		X				
Vitals		X		X	X	X
Teach use of REDCap		X				

Informed Consent Form		X				
Randomization			X			
Sociodemographic information		X				
Neurology Evaluation		X				
Headache Log		Begin	Continue	Continue	Continue	Continue
QST Heat Pain Assessments		X		X	X	X
INSTRUMENTS		X		X	X	X
Mindfulness-FFM		X		X	X	X
Emotion Regulation-DERS		X		X	X	X
Pain Catastrophizing-PCS		X		X	X	X
Pain Acceptance-CPAQ		X		X	X	X
Headache-related Disability -HIT-6		X		X	X	X

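### Part 2 repeats the heat-pain test at three follow-up visits, with no pregnancy question or skip rule set before them

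*Combined protocol and SAP*

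**What the plan says.** The pregnancy rule is in Part 1, among the exclusion criteria that apply to migraineurs and controls alike: "Pregnant subjects will be excluded from all portions of the study due to possible unknown risks of frankly noxious stimuli". The same paragraph adds, citing potential harm to the fetus, that "sexually active women of childbearing potential must use a reliable method of birth control while participating in this study". Part 1, Study Interventions, then says: "There will only be ONE study visit, which will have 3 parts".

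Part 2 has its own entry exclusion in Table 5: "Current or planned pregnancy or breastfeeding". At the Screening Visit, participants "complete quantitative sensory testing (QST) as described in Part 1", and the Part 2 Baseline Visit text gives the same stimulus temperatures, up to 49°C. The Follow-up Visits section and Data Collection Forms both place QST at all three follow-ups as well. No exception is stated.

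Eligibility is checked up to randomization. Table 8 ("Summary of Schedule of Evaluations-Part II") marks inclusion/exclusion at the telephone screen and the screening/baseline visit. The last eligibility step comes just before randomization: "Once 4-week migraine logs are reviewed by study staff to ensure eligibility". The Part 2 Study Rationale describes migraine as a condition that "principally affects women of childbearing potential".

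**The concern.** An exclusion criterion works as a safety check only if it is applied before the exposure it guards against. In Part 1 that happens automatically, because eligibility is confirmed at the start of the one visit and heat is applied at its end. In Part 2 the exposure recurs for months after the last eligibility step, and nothing in the available text prompts staff to ask again.

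A woman who conceived after baseline could therefore be given the test that the protocol says pregnant participants should not receive. The setting makes this relevant, since the protocol itself says that the condition mainly affects women who could become pregnant. What is at stake is trial conduct and adherence to the sponsor's own precaution. No estimate or error rate is involved.

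**Working it through.** No sample size, power or alpha figure is involved, so the check sets the schedule against the rule and then adds up elapsed time.

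**Schedule against rule (Part 2, Table 8 and Follow-up Visits)**

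| Visit | Inclusion/exclusion marked | QST marked | Pregnancy question or instruction to omit QST |
|---|---|---|---|
| Telephone screen | yes | no | through the eligibility criteria |
| Screening/baseline | yes | yes | through the eligibility criteria |
| Initial follow-up | no | yes | none found |
| 3-month follow-up | no | yes | none found |
| 6-month follow-up | no | yes | none found |

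The log review between baseline and randomization is also an eligibility step, but it is a review of headache diaries. The other places where a check might appear were read as well: Reporting Procedures, Potential Risks and Data Collection Forms. None contains a pregnancy question, a pregnancy test, a contraception re-check or an instruction to omit QST. The count is 3 follow-up heat sessions, of which 0 have a scheduled check.

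The protocol does write out visit-level steps elsewhere. Part 2, Reporting Procedures, has the PHQ-9 scored at every study visit, with stated actions. The Baseline Visit text has a participant with a headache rescheduled. The second of these is written for baseline only.

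**Elapsed time**

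Inputs: a 4-week headache log after baseline; 8 weeks of classes; an initial follow-up immediately after the classes; further visits 3 and 6 months later. Assumptions: no wait between randomization and the first class; 3 months taken as 13 weeks and 6 months as 26 weeks, both counted from the initial follow-up.

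Weeks from the baseline heat session:

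- Initial follow-up: 4 + 8 = 12
- 3-month visit: 12 + 13 = 25
- 6-month visit: 12 + 26 = 38

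Weeks from randomization (week 4):

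- 12 − 4 = 8
- 25 − 4 = 21
- 38 − 4 = 34

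These are minimum intervals. The trial runs in cohorts, and any wait for a cohort to start lengthens all of them. They measure the time in which a pregnancy could begin after the last check; they are not a measure of risk.

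**The case against.** The best counter-argument is that the rule already exists. If the exclusion from all portions of the study reaches the Part 2 follow-ups, it tells staff not to test a woman they know to be pregnant. If it does not reach them, testing her breaks no stated rule. This is a fair point. The carry-over is a reading of that wording and of the shared test, because Part 2 does not restate the reason. But neither branch closes the gap. On the first, the rule has no step that triggers it before heat is applied. On the second, Part 2 has only its entry exclusion, and its own text states no contraception duty, which is weaker protection.

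Second, contraception is required throughout participation and planned pregnancy is an exclusion. Both lower the likelihood. Neither is a check before the stimulus, and neither detects an unplanned pregnancy.

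Third, the documents name no specific pregnancy question at any visit, Table 8 is only a summary, and adverse events are recorded through follow-up. Silence in a summary table is indeed weak evidence. The difference is that the earlier visits at least carry an eligibility check that includes the pregnancy criterion, while the follow-ups carry none, and the follow-up narrative is silent too. Adverse event recording is not a screen before QST.

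Fourth, the hazard is described only as possible and unknown. The stimuli are brief, stay below 50°C and are stated not to damage tissue as designed. The laboratory reports more than 750 people tested without a serious adverse event from the device. This stands, and it is why the point is small.

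Finally, a self-report question will miss an unrecognised pregnancy, and the consent pages and the DSMB plan, which are not available here, may hold related instructions. Both limits are accepted.

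**Conclusion.** The concern holds, as a minor point of conduct and safety. All three follow-up heat sessions lack a scheduled pregnancy question or an instruction to omit the test. At the earliest they come about 12, 25 and 38 weeks after baseline, or 8, 21 and 34 weeks after randomization. The number of women affected cannot be derived from the documents and is likely to be small. No stated statistical figure is wrong, and the diary-based primary analysis is untouched.

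The conclusion that the protocol's own rule could be breached assumes that the exclusion from all portions of the study covers the Part 2 follow-ups. It also assumes that the unavailable documents do not already give staff an equivalent instruction. If they do, repeating it in the schedule would still put it where visit staff look.

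**What to change.** Add one row to Table 8 and one sentence to Follow-up Visits: before QST at the initial, 3-month and 6-month visits, staff ask a self-reported pregnancy-status question, and QST is not done if the answer is yes.

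A separate, optional change concerns the rest of follow-up. Read literally, the existing exclusion would also remove such a woman from the headache diary and questionnaires. If the sponsor wants her to continue with those, that wording needs amending so that only the heat test stops.

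The cost is one REDCap question at three visits, one table row and one sentence. The downside is a few missing secondary QST values, which bear on Hypothesis 2b.

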The subject population consists of 98 participants (49 migraineurs and 49 healthy controls) who will be recruited for Part I. Participants will be of any gender and ethnicity. To ensure comparable groups, participants and controls will be matched on age (± 5 yrs), gender, and race. We have obtained IRB approval for all recruitment procedures (Wake Forest IRB protocol # IRB00027845).

Participants with migraines will be recruited through several different mechanisms 1) Wake Forest Departments of Neurology, Internal Medicine, Family Medicine and Emergency Department; 2) Wake Forest [name] Headache Research Center 3) Wake Forest Electronic Medical record system; 4) Local flyers, radio/television/newspaper advertisements. The primary source of recruitment will be through the Wake Forest Department of Neurology clinics.

The primary source of recruitment will be through the Wake Forest Department of Neurology clinics. [name] has her own headache clinic within the department, where she has seen over 300 headache patients in the last year (on average 9 new and 6 follow-up patients per week). Patients will also be recruited through the Wake Forest primary care clinics. Flyers will be placed throughout the hospital and specifically in the clinics of Neurology, Internal Medicine, OB/Gyn, and Family medicine and in the Emergency Department. On average, Wake Forest sees >800 patients/year in the Emergency Department with a diagnosis of migraine.

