Sample Size Calculation: Using the marginal benefit formula for repeated measures (Vickers),⁴⁰ and assuming an average within-person correlation between repeated measurements of 0.5, a sample size of 48/group will give us 80% power to detect an effect size as low as $d=0.62$ for the group main effect (Hypotheses 1a and 1b). Thus, if the average VAS rating in the controls is 3 (± 2 SD), we will be able to detect a VAS rating of 4.24 in migraineurs; smaller differences are unlikely to have clinical significance. For hypothesis 1c, 98 participants will also give us 84% power to detect a bivariate correlation of at least 0.4 between pain catastrophizing scores or emotional reactivity scores and pain unpleasantness levels ($r \leq 0.4$ not likely of clinical significance).

Outcomes

Stimulus-response curves will be generated for each subject using the logarithmic equation: $\log(\text{VAS pain ratings}) = \log(t - 35) * \text{coefficient} + \text{intercept}$ where t represents stimulus temperature.¹ The coefficient and intercept generated for heat pain intensity and heat pain unpleasantness will both be used as outcome variables, as well as scores from the PCS and the DERS.

Data Analyses

Statistical Analyses: We will use mixed effects hierarchical regression models with a distribution and link function appropriate to the outcome (e.g., the best fitting distribution as defined by model selection). Repeated measures within each participant (i.e., experimental trials within a session) will be handled using subject-level random effects. We do not expect missing data for this Aim, given the controlled nature of the experimental session and electronic data capture. The specific analyses are outlined for each hypothesis:

Analyses 1a: We will separately regress the individual pain outcomes (pain intensity, pain unpleasantness) on the factorial effects for group (migraine, control), stimulus (43, 45, 47, and 49 C), and repeated experimental block (1, 2, and 3). Absent any higher order two-way (e.g., group x stimulus) or three-way (e.g., group x stimulus x block) interaction involving group, we will interpret a statistically significant group main effect as evidence that the two groups differ in their experimental pain reports.

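### Part 1 matches on age, gender and race, but Analyses 1a and 1b contain neither these factors nor a matched-set term, so some precision is lost and age differences within the caliper stay uncorrected

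*Combined protocol and SAP*

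**What the plan says.** Part 1, Study Enrollment Procedures, sets the design: "The subject population consists of 98 participants (49 migraineurs and 49 healthy controls) who will be recruited for Part I", and "To ensure comparable groups, participants and controls will be matched on age" (within 5 years), gender and race. The Part 1 Précis repeats the matching rule. The only reason given is comparability of the groups. The text does not say whether controls are matched individually or by frequency.

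Part 1, Data Analyses, lists the model terms:
- Analysis 1a regresses each pain outcome on "factorial effects for group (migraine, control), stimulus (43, 45, 47, and 49 C), and repeated experimental block (1, 2, and 3").
- Analysis 1b is the same model for unpleasantness, with pain intensity added.
- Analysis 1c regresses unpleasantness on stimulus, block, intensity, catastrophizing and emotional reactivity. It has no group term.

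Repeated ratings are handled by a random effect for the subject. No Part 1 analysis names age, gender, race, a pair or a matched set. The sample-size text uses only a within-person correlation and no correlation between matched participants.

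**The concern.** Matching on a factor that predicts the outcome makes the two groups positively correlated. The design has then already taken that factor's variance out of the difference between groups. A model that treats the groups as independent and omits the factor leaves the variance in the group standard error. The interval is then wider than the design warrants, and part of the benefit of matched recruitment is lost.

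There is a second, smaller issue. Age is matched only to within 5 years, so differences inside that caliper remain in the estimate of an observational comparison. Controls are sought partly through flyers at four local colleges, and migraineurs mainly through neurology clinics. A tendency for controls to be the younger member within the caliper is therefore possible.

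At stake are the group effects in 1a and 1b, which carry the Part 1 comparison of migraineurs with controls.

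**Working it through.** **Inputs from the protocol.** Part 1, Sample Size and Randomization: 48 per group, 80% power, d = 0.62, SD 2, within-person correlation r = 0.5. Experimental Session: 4 temperatures × 3 repeats = 12 ratings, or 24 if the series is given twice.

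**Assumptions.** Two-sided alpha of 0.05 (Part 1 states none). SD 2 is the SD of a single rating. R², the share of between-person variance explained by age, gender and race, is 5-15%; the documents give no figure. The model is linear.

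**1. The plan's own figure.** The plan says that "a sample size of 48/group will give us 80% power to detect an effect size as low as" 0.62 "for the group main effect (Hypotheses 1a and 1b"). The conversion to the VAS is right: 3 + 0.62 × 2 = 4.24. The power does not reproduce. With one rating per person, 48 per group and d = 0.62, a two-sample t-test has 85.2% power, and 80% power is reached at d = 0.578. Applying r = 0.5 to k ratings multiplies the variance by (1 + (k − 1)r)/k. For k = 12 this is 6.5/12 = 0.542, the detectable d is 0.425, and power at 0.62 is 98.3%. For k = 24 the power is 98.6%. The stated 0.62 is therefore conservative. That is a separate matter, but it sets the scale for any gain in power here.

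**2. Effect of adjustment on the group standard error.** With r = 0.5, half of the variance of a single rating is between persons and half within. The variance of a person's mean of k ratings is

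- unadjusted: 0.5 + 0.5/k
- adjusted for the matching factors: 0.5(1 − R²) + 0.5/k

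The ratio of standard errors is therefore sqrt(1 − R² × k/(k + 1)).

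| k | R² | SE ratio | SE cut |
|---|---|---|---|
| 12 | 0 | 1 | 0% |
| 12 | 0.05 | sqrt(1 − 0.0462) = 0.977 | 2.3% |
| 12 | 0.15 | sqrt(1 − 0.1385) = 0.928 | 7.2% |
| 24 | 0.05 | sqrt(1 − 0.0480) = 0.976 | 2.4% |
| 24 | 0.15 | sqrt(1 − 0.1440) = 0.925 | 7.5% |

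The cut is about 2-7%. Averaging over only 3 ratings gives 1.9-5.8%, and one rating gives 1.3-3.8%.

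**3. What that means on the plan's scale.** At k = 12, the difference detectable with 80% power moves from 0.425 × 2 = 0.85 VAS units to about 0.83 (R² = 0.05) or 0.79 (R² = 0.15). Power at d = 0.62 rises from 98.3% to 98.7% or 99.3%.

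**4. Direction of the error.** If the matching correlation is ignored, the test statistic has variance 1 − R² × k/(k + 1) under the null, which is below 1. At k = 12, a nominal 5% test then has true size of about 4.5% (R² = 0.05) to 3.5% (R² = 0.15).

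**5. Residual age difference.** If differences within pairs are symmetric and uniform over ±5 years (assumption), their SD is 10/sqrt(12) = 2.89 years. The mean over 49 pairs then has an SD of 2.89/7 = 0.41 years. A systematic shift could be larger, but the caliper limits it to 5 years.

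**6. Cost of the terms.** With R² = 0 and one rating per person, three added parameters move the detectable d from 0.5778 to 0.5780. A paired analysis breaks even at a within-pair correlation of about 0.02.

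**The case against.** The strongest case against is that nothing invalid is being done. Migraine status is the predictor and the rating is the outcome, so leaving out factors balanced by matching does not bias the comparison with respect to them. Any loss is on the safe side. At the plan's own d = 0.62, power is already about 98% once the repeated ratings are counted, so no Part 1 conclusion is shown to be at risk. The variance explained is unknown and may be zero. In 1b, pain intensity is already in the model and may absorb much of the same variance. The distribution and link are left to model selection, and with some links adjustment changes what the group coefficient means. Race may need several terms.

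All of this stands, and it limits the point to modest precision and a small correction for age. It does not remove the point: the model does not reflect the design, and the variables must be known in order to match.

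A reader might go further and infer any of the following, none of which the documents support:
- **The 1a and 1b tests have inflated type I error.** Ignoring a positive matching correlation has the opposite effect.
- **The flaw extends to the group standard error in 1c.** That model has no group term.
- **The factors were chosen because they affect pain.** The protocol gives only comparability as its reason.
- **The controls are systematically younger.** The recruitment sources make this possible, but do not show it.

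**Conclusion.** The point holds as a matter of efficiency, not validity. Part 1 is matched by design, and Analyses 1a and 1b carry no trace of the matching. If age, gender and race relate to pain ratings, the group standard error is conservative, and age differences within the caliper are left uncorrected.

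The likely size is a cut of about 2-7% in the standard error for 1a. This rests on R² of 5-15% of between-person variance, which is assumed, the plan's r = 0.5, 12 to 24 ratings averaged, and a linear model. The cut is nil at R² = 0 and probably smaller in 1b. The direction does not depend on the assumed figure, provided the factors are prognostic at all. Covariate adjustment is suitable whether matching was individual or by frequency.

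**What to change.** - **Analyses 1a and 1b:** add age (continuous), gender and race as subject-level fixed effects, with a prespecified grouping of race if categories are sparse.
- **Matching:** state whether it is one-to-one. If it is, record the pair and add a matched-pair random effect in 1a and 1b.
- **Non-linear link:** if model selection leads to one, say whether the adjusted or the unadjusted group effect is the one to be interpreted.
- **Analysis 1c:** the same covariates may be added as potential confounders of the associations of catastrophizing and emotional reactivity with unpleasantness. The matching is not the reason, since it does not balance these factors across levels of the two scores.

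No new data are needed, because the matching already requires these variables. The loss of degrees of freedom is negligible. Fixing the terms before analysis also prevents a later choice between adjusted and unadjusted results.
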